
Objective

In this clinical trial, we evaluated the effectivity of three non-invasive analgesic techniques (cold, anesthetic cream and vibration), including a control zone, in 100 healthy individuals, by performing subcutaneous forehead injections of 0,1ml physiologic saline.

Hypotheses

[figure not shown]
Any of the analgesic methods improves pain control respect to not utilizing any of them.

Our second aim is to evaluate if any of the analgesic methods evaluated achieves a better pain control than the others.

Randomization details

The sequence of infiltration zones of each subject was randomized through simple randomization, performed by the statistic department of the Medical Research Institute Hospital La Fe.

CONSORT Flow Diagram

Interim analysis

Performed by: [name]

Date: 16/03/2019

An interim analysis was performed when 50 subjects had already been recruited. A sample size of 46 subjects (184 interventions) was estimated, assuming a variance in the values of the control zone of 2,69, with a precision of 1, confidence level of 95%, and statistical power of 0,9.

No modifications were performed to the protocol after the interim analysis.

Guidelines for stopping study early: None

Date of final analysis: 30/04/2019

No protocol deviations were detected

Intervention adherence was not necessary as no follow-up was required

Population analyzed

From the 100 healthy subjects included in the study, 61 were females and 39 males. The average age was 39,71 (sd 13,22).

Exclusion criteria

- Chronic pain syndromes/conditions
- Receiving opioid analgesics and sedatives
- Extreme sensitivity to cold
- Allergy to components of the anesthetic cream EMLA (eutectic mixture of lidocaine; 2,5% lidocaine and prilocaine 2,5%)
- Inability to understand the visual analogic scale

Inclusion criteria

Every subject that did not meet any of the exclusion criteria, and signed the informed consent, was included in the study

Recruitment strategy

Adult employees and volunteers at The University and Polytechnic Hospital La Fe that understood the study and signed the informed consent were eligible for participation.

We did not have any case of **withdrawal** from the study

Material and methods

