This study is a randomized, controlled, simple-blind clinical trial, and it has been approved by the Ethics Committee of the Medical Research Institute Hospital La Fe. The study included 100 healthy volunteers, and it was performed at the University and Polytechnic Hospital La Fe, Valencia.

The procedures of the study consisted in the sequential performance of four injections of 0,1mL of physiologic saline (0,9%NaCl) in the forehead of each subject, 2cm above the eyebrows, with a 29G needle, after applying each one of the non-invasive analgesic methods studied in the trial, except for the control zone. The anesthetic method utilized in each part of the forehead of each patient was randomized through simple randomization. Injections always started from the right side of the forehead to the left. The non-invasive analgesic methods utilized were:

- Control zone (A): None
- Vibration (B): Application of the vibrating device on the skin below the injection site, before and during injection.
- Cold (C): Application of a bag of 50mL of frozen physiologic saline covered with a plastic glove on the injection site for 50 seconds prior to performing the injection.
- Anesthetic cream (D): Application of a uniform thickness of 2mm of the anesthetic cream EMLA covered with an adhesive transparent plastic dressing for 30 minutes, before injection.

Results were evaluated through surveys that included demographic data (initials, gender, age), a Visual Analogic Scale (VAS) with a maximum value of 10 and minimum of 0 for pain evaluation of each of the four injected zones of each subject. Also, two direct questions were included, one with the aim of determining the preferred method for each subject for future injections (“Which anesthetic technique would you prefer if you had to be injected again?”), and another to report discomfort related to the application of any of the anesthetic procedures (“Did any of the anesthetic methods cause you pain or discomfort?”)

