An interim analysis was performed when 50 subjects had already been recruited. A sample size of 46 subjects (184 interventions) was estimated, assuming a variance in the values of the control zone of 2,69, with a precision of 1, confidence level of 95%, and statistical power of 0,9. The statistical study included a Friedman test for evaluating the existence of differences between the average results of each different anesthetic method and control zones, and to evaluate the existence of differences in pain referred depending on the injection order, or the side of the forehead injected (central or lateral). After finding statistically significant differences between average pain referred with different techniques, paired comparisons were performed between each non-invasive anesthetic method with a Wilcoxon test. For comparison of average pain according to subject gender, a Mann-Whitney U test was utilized. Statistical analysis was performed by a researcher that did not participate in the practical part of the study ([name]) utilizing the software SPSS.

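### Injection number and forehead site are one factor because every subject was injected right to left, so the planned injection-order test is equally a test of site (secondary tests only)

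*Combined protocol and SAP*

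**What the plan says.** Under Material and methods, each subject receives a "sequential performance of four injections of 0,1mL of physiologic saline (0,9%NaCl) in the forehead of each subject, 2cm above the eyebrows". The direction is fixed: "Injections always started from the right side of the forehead to the left". What varies at random is the technique: "The anesthetic method utilized in each part of the forehead of each patient was randomized through simple randomization". Randomization details words it differently: "The sequence of infiltration zones of each subject was randomized through simple randomization".

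The statistical paragraph of the same section uses a Friedman test to compare techniques and also "to evaluate the existence of differences in pain referred depending on the injection order, or the side of the forehead injected (central or lateral"). It does not say that order and site coincide, or how four scores are reduced to central and lateral. Both aims under Hypotheses concern techniques; the second reads "Our second aim is to evaluate if any of the analgesic methods evaluated achieves a better pain control than the others".

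**The concern.** The sites lie at one height and are always worked through in one direction, so the first injection is always the rightmost site and the fourth always the leftmost. Nothing in the design varies order while holding site fixed, or the reverse. The plan nevertheless lists order and site as separate questions.

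What is at stake is attribution. A significant order test could be reported as sensitization, habituation or anticipation when the cause is anatomical. A significant central/lateral test could be reported as anatomical when the cause is that the first needle hurts most. In either case the detected difference is real, but the stated reason for it may be wrong.

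**Working it through.** **Inputs from the document (Material and methods).** Four injections per subject, fixed right-to-left direction, technique randomized to site, 100 subjects, control-zone variance 2.69 ("assuming a variance in the values of the control zone of 2,69, with a precision of 1").

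**Assumptions.** Sites in the order lateral, central, central, lateral (no site map is in the available text, and figures were not extracted); normal scores with variance 2.69 at every site; within-subject correlation ρ from 0.3 to 0.7; each technique 1 point below control; central and lateral compared through each subject's two-site means. The document gives no effect size for order or site, so 0.5 and 1 point are illustrative.

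**The plan's own figure.** There is none for order or site. The stated 46 subjects is recovered by a one-sided, independent-groups formula, 2 × 2.69 × (1.645 + 1.282)² / 1² = 46.1, and 46 × 4 = 184. It does not bear on this point.

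**Step 1: aliasing.** An intercept, three order indicators and three site indicators make 7 columns, but over the four positions their rank is 4. The site columns repeat the order columns. A Friedman test by order and one by four-level site use the same four scores under different labels. This needs no assumption about layout or effect size.

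**Step 2: the central/lateral contrast.** With position means m1 to m4 and the assumed layout, L = (m1 + m4)/2 − (m2 + m3)/2.
- Lateral effect a: L = (a + a)/2 = a.
- First-injection effect f: L = f/2.
- Linear order trend s per step: L = (0 + 3s)/2 − (s + 2s)/2 = 0.
- Fading order effect 1, 0.5, 0.25, 0: L = 0.5 − 0.375 = 0.125.

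**Step 3: how often a first-injection effect alone makes central/lateral significant.** For one subject, Var(L) = 2.69(1 − ρ) + 0.25. The 0.25 arises because the control condition, 1 point higher, falls on a lateral or a central site at random and moves L by ±0.5. A two-level Friedman test is a sign test. With 100 subjects it is significant when at least 60 subjects (or at most 40) have L above zero, since (2 × 60 − 100)²/100 = 4.00 exceeds 3.84. The chance that L is above zero is about Φ((f/2)/SD).

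| ρ | Var(L) | SD | f = 0.5: Φ(0.25/SD) | significant | f = 1: Φ(0.5/SD) | significant |
|---|---|---|---|---|---|---|
| 0.3 | 2.133 | 1.460 | 0.568 | 29% | 0.634 | 79% |
| 0.5 | 1.595 | 1.263 | 0.578 | 37% | 0.654 | 89% |
| 0.7 | 1.057 | 1.028 | 0.596 | 51% | 0.687 | 97% |

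Simulation (6,000 runs per cell) gives 30%, 37% and 50% for f = 0.5, and 79%, 89% and 97% for f = 1. Under a linear trend of 0.3 per step the rate stays near the nominal 5%.

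**Step 4: the reverse direction.** With a pure lateral effect of 0.5 point and no order effect, the order Friedman test is significant in 83% of simulated trials at ρ = 0.5 (69–95% for ρ from 0.3 to 0.7).

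**Step 5: the technique comparison.** With a true technique difference of 1.00 and a first-injection effect present, the mean estimate across simulated scenarios is 0.99 to 1.01. No bias appears.

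**The case against.** The strongest reply is that the plan makes no false claim. It asks whether pain differs by order or by side, and nowhere says that the two can be separated or that a difference would be due to repeated injection. If the tests are only checks for some position effect, the aliasing costs nothing. This stands in part: the harm arises only if results are attributed, and it is why the point is minor. It does not remove the point, because two named questions invite two separate answers that the design cannot give.

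The layout objection also stands. The half share and the rates in Steps 3 and 4 depend on an order of sites that the available text does not state. The aliasing in Step 1 does not. The rates further depend on assumed effects; 1 point is as large as the difference used for the sample size.

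A reader might infer more than the documents support:
- *That the fixed direction biases the technique comparison.* It does not. Technique was randomized to site, and chance imbalance adds only noise.
- *That order and central/lateral can never be told apart.* They can under restrictions: no left-right site gradient and a restricted order pattern. An order trend cannot be separated from a right-to-left gradient or from an unrestricted four-level site effect.
- *That Randomization details contradicts Material and methods.* Its sentence can be read as a randomized injection path. But the document calls a treatment condition a control zone, so zone there can mean technique, and the two statements then agree.

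**Conclusion.** The point holds, as a minor one confined to secondary tests. Injection number and four-level site are fully aliased; this follows from the stated direction alone. The order test is equally a site test, and a significant result supports neither explanation over the other.

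Conditional on the lateral, central, central, lateral layout, the central/lateral comparison is protected against a linear order trend but carries half of any first-injection effect, so it is not a purely anatomical comparison. The size of that problem is uncertain: about 30–50% false attribution to site for an assumed 0.5-point first-injection effect, and 79–97% for 1 point. The conclusions on techniques are unaffected.

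**What to change.** 1. Replace the separate order and site questions with one within-subject position analysis (3 degrees of freedom) adjusted for technique. A rank-based version on technique-adjusted scores is enough. Label the result as position, order and site combined, and draw no conclusion about order alone or site alone from it.
2. Keep the planned central/lateral contrast, with a confidence interval. State the site layout, and state that under it the contrast is free of a linear order trend but not of a first-injection effect.
3. Do not substitute piecewise comparisons. Injection 4 against the mean of 2 and 3, for example, removes the first-injection effect but is significant in 79% (68–93%) of simulated trials under a linear trend of 0.3 per step, where the planned contrast stays near 5%.
4. A model with first-injection and linear-order terms is at most an optional sensitivity analysis, with its restrictions stated. Its lateral term is m2 − 2m3 + m4. At ρ = 0.5 the error variance is 2.69 × 0.5 = 1.345, so the standard error is √(6 × 1.345/100) = 0.284, against √(1.345/100) = 0.116 for the planned contrast, or 2.45 times larger. Simulated power for a 0.5-point lateral effect falls from 99% to 42%.
5. Optionally, clarify in Randomization details that technique was randomized to site and the injection direction was fixed.

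The cost is slightly more analysis and weaker secondary claims. No new data are needed.

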Evaluation of Three Non-invasive Analgesic Techniques in Pain Prevention During Injections

Clinicaltrials.gov - NCT03974633

Date of last Statistical Analysis Plan edition: 19/08/2019

- Performed in order to adapt the protocol to the requirements of registration at clinicaltrials.gov

Date of previous Statistical Analysis Plan: 08/06/2018

Protocol version 2.0

Person writing SAP: [name]

SAP Contributors: [name]

Senior statistician: [name] (blind researcher)

Principal Investigator: [name]

Investigators participating in the practical part of the study:

- [name]
- [name]
- [name]
- [name]

Background

The application of injectable substances, whether local anesthetics, vaccines, drugs or cosmetics, can cause significant pain and discomfort. There exists a wide range of variables that may influence the subjective experience of each patient during the performance of an injection, like the type of substance utilized, the volume of liquid infiltrated, the anatomic location, or whether a non-invasive anesthetic technique is utilized (1).

As regards traditionally used non-invasive analgesic techniques for pain control during injections, there are a limited amount of clinical trials that provide an adequate level of evidence in this field (1). Some studies claim to have proven the efficacy of cold, anesthetic creams or vibration for pain control during injections (2). Notwithstanding, these studies have generally focused in comparing only the studied analgesic technique with a control group, instead of comparing anesthetic techniques among themselves (2). Furthermore, it is even scarcer the amount of studies focused in the field of cosmetic subcutaneous injections; whereas most of the reported studies have been performed in the context of anesthetic injection in odontology, intravitreal injections, or blood sample collection in pediatric population (3).

The use of cold for pain control during injection has been traditionally utilized in different contexts. Notwithstanding, scientific evidence in favor of the use of cold as an analgesic agent in the context of injections is scarce, and has a low level of evidence (4). The mechanisms through which cold is considered to elevate pain threshold are: an alteration of nerve conduction, reduction of muscle spasms and prevention of tissue edema (4-6).

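### No multiplicity adjustment is stated for the pairwise Wilcoxon tests; if the three techniques are equal and control is worse, a false difference between techniques has about a 12% chance

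*Combined protocol and SAP*

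**What the plan says.** The Objective describes a within-subject comparison of "three non-invasive analgesic techniques (cold, anesthetic cream and vibration), including a control zone, in 100 healthy individuals". The Hypotheses section states two aims. The first is that "Any of the analgesic methods improves pain control respect to not utilizing any of them". The second is worded: "Our second aim is to evaluate if any of the analgesic methods evaluated achieves a better pain control than the others".

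The last paragraph of Material and methods specifies a Friedman test across the techniques and control. After a significant result, "paired comparisons were performed between each non-invasive anesthetic method with a Wilcoxon test". Neither this paragraph nor any other part of the document gives an adjustment for multiple testing, a per-test significance level or the sidedness of the Wilcoxon tests. The 95% confidence figure belongs to the sample-size statement.

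The number of pairs is not explicit. In Material and methods, the list introduced by "The non-invasive analgesic methods utilized were" opens with "Control zone (A): None", which points to four conditions and six pairs. The sentence describing the Wilcoxon tests, read alone, could mean only the three technique-versus-technique pairs.

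On timing, the document records "Date of final analysis: 30/04/2019" and "Date of last Statistical Analysis Plan edition: 19/08/2019".

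**The concern.** Unadjusted pairwise tests after a significant omnibus test control the familywise error with three conditions. With four they do not. The Friedman test limits false claims to 5% only when all four conditions are equal. Once one condition truly differs, the gate opens because of that condition and no longer restrains the comparisons among the rest.

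The first hypothesis expects control to hurt more than the techniques. If it does and the techniques are equally good, the Friedman test is significant almost every time, and three true null hypotheses (cold–cream, cold–vibration, cream–vibration) are then each tested at full alpha. Those three comparisons are the substance of the second aim, so a chance finding there could be reported as one technique being superior to another.

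**Working it through.** **Inputs.** From the document: four conditions, N = 100, variance 2.69 (SD √2.69 = 1.640), a difference of 1 point, and the Friedman-then-Wilcoxon rule. Assumed, because not given: two-sided 5% per test, and a within-subject correlation varied from 0 to 0.7.

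**The plan's own figure.** For two independent means, n = 2σ²(z_α + z_β)²/δ². One-sided 5% and power 0.9 give 2 × 2.69 × (1.645 + 1.282)² = 46.07, which matches the stated 46. Two-sided gives 2 × 2.69 × (1.960 + 1.282)² = 56.5, which does not. So the sample size appears to rest on a single one-sided comparison, with no allowance for several.

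**Analytic check.** With three equal techniques and the gate open, a false claim occurs when the largest and smallest technique means differ by more than 1.96 standard errors of a difference. In studentized-range terms this is P(range of 3 > 1.96 × √2) = **12.2%**. Treating the three tests as independent gives 1 − 0.95³ = 14.3%, which is too high because the tests share conditions.

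**Simulation of the stated rule.** Tie-corrected Friedman test at 5%, then two-sided signed-rank tests at 5%. With control 1 point worse, N = 100 and 20,000 trials per setting (correlation 0 or 0.5; continuous or integer scores):

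- the gate opens in 98% to 100% of trials;
- at least one false technique-versus-technique claim occurs in 11.7% to 12.4% (Monte Carlo standard error √(0.12 × 0.88/20,000) ≈ 0.2 points);
- Holm over six pairs reduces this to about 3.9%.

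Smaller runs at correlations from 0 to 0.7 gave 10.6% to 13.0%, scattered around the analytic value.

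**Other configurations** (mean pain for control/three techniques, correlation 0.5, scores rounded to 0.5, about 4,000 runs each):

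| Means | Any false technique pair | Any false claim, six pairs | Holm over six |
|---|---|---|---|
| 4.5/4/4/4 | 11.2% | 11.2% | 3.3% |
| 5/4/4/3 | about 5% | about 5% | about 5% |
| 4/4/4/4 | 3.5% | 4.9% | below 5% |
| 4/3/4/4 | 4.7% | 11.8% | 4.0% |
| 4/4/3/3 | 4.5% | 9.5% | 4.7% |

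At correlation 0.3 the first row falls to 9.8% unadjusted and 2.3% with Holm. In the second row there is one true null tested at 5%; two runs gave 4.1% and 5.2%.

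A stricter false claim, one technique beating both others when all three are equal, occurs in only about 1.4% of runs.

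**The case against.** The strongest counter-case has four parts.

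- **The second aim can be read more narrowly.** If it means that one technique beats both others, the false-claim rate is about 1.4% when all three are equal, and near 5% when two tie for best. Under that reading unadjusted testing does little harm. This stands as a reading. But the plan tests pairs one at a time and does not require a technique to win both comparisons, so a single significant pair could be reported as a difference.
- **The 12% belongs to one configuration.** Correct: among those examined, only three equal techniques with a worse control takes the technique pairs above 5%. It is nevertheless a case the first hypothesis makes plausible. If the technique-versus-control pairs are also tested, the error reaches 11.8% when only one technique works.
- **The family may be three pairs, and cheaper remedies exist.** The wording is ambiguous. The 12% does not depend on it, because technique-versus-control pairs are not true nulls in that case. Holm over the three technique pairs (3.5% in a check run), or a second Friedman test on the three techniques alone (3.6%), would control the technique-pair error at less cost in power. Neither covers the comparisons with control, which the first hypothesis needs because a Friedman test does not say which technique beats control.
- **Sidedness is unstated, and a correction may have been used.** Both are true. The figure is conditional on two-sided 5% tests, and silence does not prove that no correction was made.

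**Conclusion.** The concern holds. As written, the rule does not control the familywise error across the pairwise comparisons. If the three techniques are equal and control is 1 point worse, the chance of at least one false technique-versus-technique claim is about 12%, more than twice the nominal 5%. With control only 0.5 point worse it is about 10% to 11%. These figures assume two-sided 5% tests; the simulations also assume variance 2.69 and N = 100, and the result changes little across correlations from 0 to 0.7. About 12% is near the maximum, not a typical value.

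The absence of a stated adjustment is certain. Its effect on the trial's conclusions is not, because the document gives no pain results. The point should be fixed: it bears on a declared aim and needs no new data.

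**What to change.** Add a sentence to the statistics paragraph: all six pairs (three technique-versus-control, three technique-versus-technique) are tested with two-sided Wilcoxon signed-rank tests, Holm-adjusted over the six at 5%, and adjusted p-values are reported. This covers both aims and is valid whether three or six pairs were intended. If a correction was used, name it and its family of tests instead.

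Apply the adjustment to the existing data and label it post hoc, since the final analysis (30/04/2019) precedes the last SAP edition (19/08/2019). Any ranking of techniques that does not survive the adjustment should not be presented as confirmed.

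The cost is one SAP sentence, recalculated p-values and some power. At N = 100, even at the strictest Holm step (0.05/6 = 0.0083), power per pair for a 1-point difference is 93% at correlation 0, 99% at 0.3 and above 99% at 0.5. The loss is real for a 0.5-point technique-versus-control difference: from about 75% to 62% at correlation 0.5, or from about 55% to 42% at 0.3.
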